The Effect of Combining Spinal Manipulation and Dry Needling in  
Individuals with Non-specific Low Back Pain

Study Protocol and Statistical Analysis Plan

Approved until 12/10/2023

This study will use a randomized comparative design with three intervention groups in individuals with nonspecific LBP. The first patient-reported outcome to be assessed is disability, assessed with the LBP Oswestry Disability Index Questionnaire (ODI). The ODI score is derived from the Oswestry Disability Questionnaire, resulting in a score ranging from 0-100 with higher numbers indicating a greater level of disability [84]. Patient-centered outcome measures represent the majority of clinical nonmechanistic measures from the view and disability outlook of the patient. They are an effective way for the patient to explain the degree of pain and disability being experienced from LBP.

The second patient-reported outcome will utilize the pain rating score derived from the numeric pain rating scale (NPRS) to evaluate pain intensity throughout the trial. Participants will be asked to make separate ratings of current pain intensity and the best and worst intensity over the past 24 hours on a 0-10 scale (“0” no pain and “10” worst imaginable pain). The mean of the three ratings will be used to represent pain intensity.

The mechanistic outcome measures include LMM, ES, and GM muscle activation measured by changes in contraction thickness at rest and sub-maximal isometric contraction. The primary comparison will consist of the combination group compared against each single treatment group of SMT or DN in order to evaluate the advantage of utilizing both modalities together. This study will further perform a secondary exploratory comparison of the SMT and DN only groups. The primary comparison time-point will evaluate these outcome measures at 4-weeks (late effect) compared to baseline and a secondary comparison (early effect) at 2-weeks with comparison being controlled for baseline value. A third comparison time-point will be evaluated at 1-week consisting of

only patient-reported outcomes to assess initial effects of treatment on reported pain. All patient-reported outcomes will be assessed 48 hours following the second and fourth treatment sessions. The duration of the trial intervention for a participant will be four weeks from initial baseline assessment. Participants will be randomly assigned to one of three intervention groups for the first 2 weeks of treatment: combination of SMT and DN, DN only, and SMT only. Each treatment group will receive two treatment sessions per week for the first two weeks with NPRS and ODI measures assessed at baseline, 1-week, and 2-weeks. The third and fourth weeks will consist of an at home exercise program with NPRS and ODI measures taken at the final assessment at the end of the fourth week. Diagnostic ultrasound measures of the LMM, ES, and GM muscles will be taken at baseline and post-treatment following the fourth and final assessment sessions.

#### *Randomization and data collection*

Randomization will be conducted utilizing REDCap in order to conceal sequence from participants and researchers. Participants will be randomized into one of three treatment groups. The use of standard protocols and compliance audits throughout the study will be utilized to minimize potential bias. Study data will be collected and managed using REDCap electronic data capture tools hosted at the University of Utah.

#### *Outcome measures*

After attaining informed consent, participants will complete a baseline assessment. Participant demographics, age, gender, race/ethnicity, body mass index, marital status, employment status, highest education level, current and past LBP

interventions, and a physical examination will be collected and performed. The physical examination will include various tests designed to ensure proper study inclusion and to identify the most symptomatic side (right or left) and most symptomatic levels (L3, L4, or L5) for treatment and outcome assessment.

LMM, ES, and GM muscle activation will be measured with brightness-mode ultrasound images using a Sonosite MicroMaxx (Sonosite Inc. Bothell, WA, USA) and a 60-mm, 2–5 MHz curvilinear array or a Butterfly iQ+ (2020 Butterfly Network Inc., Burlington, Massachusetts) with both using a validated protocol. Measures for the LM will be taken with the participant in the prone position. The ultrasound transducer will be placed just lateral to the spinal midline and angled medially until a parasagittal view of the multifidus muscle is obtained. Images will be obtained at the most symptomatic side and level with the muscles at rest and during submaximal contraction in response to the participant raising the contralateral arm about two inches while holding a weight proportional to body weight, resulting in approximately 30% maximum voluntary isometric LMM contraction. Measurements at rest and contracted will be taken three times at the treatment sites. Offline measures of the multifidus muscle activation will be obtained for both the resting and contracted states from determining the distance between the posterior-most aspect of the facet joint inferiorly and the plane between the multifidus and thoacolumbar fascia superior. Images of the GM muscle will be obtained with the transducer positioned midway between the posterior iliac spine (PSIS) and the greater trochanter. Thickness measurements will be taken between the ischium and the fascial plane between the GM and gluteus maximus muscles along the mid-axillary line and the middle of the muscle belly centered within the field of view. The ES muscle will

be imaged following techniques used with the transducer positioned on the bulk of the muscle immediately above the iliac crest centered on the symptomatic side and spinal level. The transducer will be oriented in the sagittal plane so that it is roughly parallel to the muscle fibers and angled slightly medially to optimize image clarity. Muscle activation will be calculated as the change in thickness at rest and submaximal contraction ( $\text{Thickness}_{\text{contracted}} - \text{Thickness}_{\text{rest}}$ ) / ( $\text{Thickness}_{\text{rest}}$ ). The average of the three measures will be calculated at each treated symptomatic spinal level. All muscle thickness measures will be downloaded and performed offline on a different date from when the images are obtained utilizing Image J software (V1.38t, National Institutes of Health, Bethesda, Maryland) [85]. The researcher performing the offline muscle thickness measures will be blinded to participant treatment group allocation and measurement timepoint in order to control for any potential measurement bias.

#### *Intervention groups*

This study will involve three intervention components provided in different sequences and combinations for four weeks. Following baseline assessment, each study participant will be randomized to a treatment group to receive SMT, DN, or a combination of DN and SMT. Each treatment session will begin with a brief assessment by the clinician to assure the participant has remained appropriate to receive treatment.

All SMT treatment sessions will be provided using protocols applied in previous studies investigating clinical outcomes and mechanism of effect. The preferred SMT technique will be performed with the participant supine. The clinician will stand opposite the side to be manipulated and side-bend the participant. The side to be manipulated will be the side identified as more painful. The participant will then interlock their fingers

behind the head. The clinician will then rotate the participant and deliver a high-velocity, low-amplitude (HVLA) thrust to the anterior superior iliac spine with a posterior/inferior direction. The clinician will note if a cavitation (i.e. a “pop”) occurs and record which attempt and side that it occurred. Each participant receiving SMT will have two attempts per side performed regardless of when a cavitation occurred. If no cavitation occurs on any attempt this will also be noted. The substitution of the supine position for the side-lying technique will be permitted based on participant preference or comfort. Once participant preference is determined at the baseline examination the chosen technique will be used for the duration of the trial for that respective participant.

DN treatment will be performed in the ES, GM, and LM at the most symptomatic side and spinal levels determined at baseline examination. If the clinician is unable to determine the most symptomatic levels or areas, treatment will be performed to the middle of the ES and LM bellies at the L4 and L5 levels and the ipsilateral GM. General needle technique utilized for all muscles will include insertion of a sterile, disposable, solid filament steel needle (Seirin Corp., Shizuoka, Japan) into the desired muscle. The size of the needle will be either 0.25 x 50mm or 0.30 x 60mm based on the size of the participant. “Clean needle technique” will be used throughout the treatment procedures which included hand washing, clean latex-free nitrile exam gloves, and cleaning the participants skin with an alcohol swab prior to treatment. The needle technique that will be utilized for the LM is to start at approximately 1.5 cm lateral to the spinous process angling approximately 15-20 degrees medially and slightly inferior inserting the needle into the depth of the muscle until the lumbar lamina was reached. For the ES muscles, the needle will be inserted just lateral to the paraspinal muscle bulk (approximately 5-10

cm lateral to the spinous process) in the lateral to medial direction towards the spinous process. The GM will be needled in the upper lateral quadrant of the buttock between the region proximal to the greater trochanter and inferior to the iliac crest. The needles will remain in the muscle for 10 minutes with needle manipulations being delivered every 2 minutes to elicit a local twitch response.

Exercise sessions will consist of a series of LM exercises targeting isometric muscle contraction and activation. Specific exercises were selected that not only activated the LM, but also the GM and ES muscles. Following the fourth treatment session, the participant will be assigned a home exercise program consisting of isometric multifidus contractions in different positions with initial clinician feedback and exercises to isometrically co-contract the multifidus and deep abdominal muscles. Participants will also perform lumbar extensor strengthening exercises shown to produce 20-50% multifidus maximum voluntary contraction. Participants will continue to perform the assigned exercises through the third and fourth weeks at home up until the final assessment. The prescribed exercises and participant compliance with assigned exercises will be recorded at the final assessment session.

There is little to no research on which therapy should precede the other in the combination SMT and DN group, and instead of leaving it up to clinician preference and to maintain consistency in treatment, SMT was designated to be performed first with DN following manipulation therapy. Following the two-week intervention period of SMT and DN, DN, or SMT the participants will begin the second phase of treatment consisting of two weeks of at home activation/strengthening exercises for two weeks.

#### *Statistical methods*

The study treatments will include spinal manipulation therapy (SMT), dry needling (DN), and exercise (EXER). Participants will be block randomized in sizes of 3 and 6 into three study groups: (SMT+EXER), (DN+EXER), and (SMT+DN+EXER). Repeated measurements of the outcomes will be collected at baseline, two weeks post-treatment, and four weeks post-treatment. The first primary outcome is the continuous variable Oswestry Disability Index (ODI). The second primary outcome is the continuous variable 0-10 numeric pain rating scale (NPRS). The primary time point is at four weeks (late effect) and the secondary time point is at two weeks (early effect). To determine if (SMT+DN+EXER) is superior to (SMT+EXER) on the ODI outcome, a linear regression model will be fitted using the 2-week ODI as the outcome variable, group as the primary predictor [(SMT+DN+EXER) vs (SMT+EXER)], and baseline ODI as a covariate, in an analysis of covariance (ANCOVA) fashion. In a similar model, (SMT+DN+EXER) will be compared to (DN+EXER). All comparisons will be made at the alpha 0.05 level.

Exercise compliance will be measured by participants self-reporting adherence to the program by selecting average number of days per week the exercises were completed. Self-reporting will take place during the final visit at the end of the fourth week. Participants will be informed of this method of self-reporting compliance in order to aid in tracking adherence over the two-week period.

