#### *Sample size justification*

For a simple comparison of a post (week 2) standardized (z-score) outcome variable, which is the standardized outcome variable in the ANCOVA model, mean +/- SD: 0 +/- 1 versus 0.64 +/- 1 (that is, a 0.64 SD difference), we required n= 41 per group to achieve 80% power using a two-sided alpha 0.05 comparison. We assumed a

correlation of  $r = .50$  between the baseline and post-treatment outcomes, which was a reasonable assumption given that changes over two weeks would mostly be in the improvement direction, with minimal patients changing in the opposite direction. The  $n=40$  per group sample size was next adjusted to account for the increased power achieved by the ANCOVA approach [180]. In doing this, the  $n = 40$  was multiplied by the factor  $(1 - r^2) = (1-0.50^2) = 0.75$ , so we only required  $n = 40 \times .75 = 30$  per group to achieve the same effect size. Based on prior work of 92% retention to a four-week trial, a sample size of  $n=99$ , 33 per group, accounts for potential participant drop-out [20,168]. This planned sample size works if a 0.64 SD difference is likely or represents at least a minimal clinically meaning difference. In a DN study, baseline ODI was mean  $+\text{- SD } 31.5 \text{ } +\text{- } 11.5$  which decreased to  $23.4 \text{ } +\text{- } 13.5$  one-week post-treatment, a mean difference divided by pooled SD, while assuming  $r=0.50$ , of  $(23.4 - 31.5)/12.6 = -0.64$  SD difference. In the same study, although a difference in NPRS was not reported, baseline NPRS mean  $+\text{- SD}$  was  $5.0 \text{ } +\text{- } 1.7$ . A 0.64 SD improvement would be  $(5.0/1.7) \times 0.64 = 1.9$  point change. This reduction in pain would be noticeable and beneficial to the patient, and so is at least a minimally, clinically relevant effect size [181]. In a SMT study [51,182], reported baseline ODI mean  $+\text{- SD } 32.2 \text{ } +\text{- } 11.9$  which decreased to  $23.9 \pm 11.4$  post-treatment, a  $(23.9-32.2)/11.7 = -0.71$  SD difference. So, both DN and SMT achieve a 0.64 SD effect size by themselves. However, our study specifically tested if DN+SMT is superior to DN and is superior to SMT. Individual participant response to only DN or only SMT could vary, with some level of synergy of DN+SMT being more effective than the sum of the individual effects. Therefore, we used the 0.64

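### Four weeks is the declared primary time point, but the only efficacy model written down, and the sample size, use the 2-week outcome

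*Combined protocol and SAP*

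**What the plan says.** The design overview at the start of the document sets the order of the visits: "The primary comparison time-point will evaluate these outcome measures at 4-weeks (late effect) compared to baseline", followed by "a secondary comparison (early effect) at 2-weeks with comparison being controlled for baseline value". Statistical methods repeats it: "The primary time point is at four weeks (late effect) and the secondary time point is at two weeks (early effect".

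The next sentence of Statistical methods then specifies the ODI comparison of the combination arm with the manipulation arm: "a linear regression model will be fitted using the 2-week ODI as the outcome variable", with group as predictor and baseline ODI as covariate. The comparison with the needling arm follows by reference: "In a similar model, (SMT+DN+EXER) will be compared to (DN+EXER". No other visit is named for it.

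Sample size justification opens with "For a simple comparison of a post (week 2) standardized (z-score) outcome variable, which is the standardized outcome variable in the ANCOVA model". It assumes a baseline-to-outcome correlation of r = 0.50 and defends that value by what is expected over two weeks.

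On timing, the design overview states: "All patient-reported outcomes will be assessed 48 hours following the second and fourth treatment sessions". The fourth session closes the two-week treatment phase. Under Intervention groups, the home exercise programme is assigned after that session and carried out in weeks three and four.

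**The concern.** The plan declares one time point and models another. An analyst who follows the written model tests the early effect. An analyst who follows the declared hierarchy tests the late effect, but has to construct the model. Both could say that they followed the plan, so the choice can be made after the results are known.

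The two visits also answer different questions. All three arms carry an exercise component in their names, but at week 2 participants have had almost none of the home programme. The week-2 contrast is therefore manipulation and needling before exercise. Only the week-4 contrast compares the full regimens.

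Finally, the claimed 80% power was worked out for the week-2 outcome. Whether it carries over to the declared primary endpoint is not shown.

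**Working it through.** **1. Does 2-week mean the same thing throughout?** Statistical methods dates its visits as two and four weeks post-treatment. Treatment ends at about week 2, so two weeks after treatment would be week 4 from baseline, and the 2-week ODI might have meant the final visit. That reading fails for two reasons. The same paragraph defines two weeks as the secondary, early effect. Sample size justification says week 2 outright and identifies that variable as the outcome of the ANCOVA. On this labelling, four weeks post-treatment would also fall at about week 6, after participation ends at week 4.

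**2. Reproducing the plan's sample size.** Inputs from Sample size justification: difference 0.64 SD, SD 1, two-sided alpha 0.05, power 80%, r = 0.50, retention 92%.

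- Unadjusted: n = 2(1.960 + 0.842)² / 0.64² = 38.3, so 39 per group. The t-test solution is 39.3, so 40. The plan states 41, then carries 40 forward.
- ANCOVA factor: 40 × (1 − 0.50²) = 40 × 0.75 = 30.
- Dropout: 30 / 0.92 = 32.6, so 33 per group and 99 in total.

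The plan's figure reproduces. The arithmetic is sound, but it describes week 2.

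**3. Power at week 4.** The documents give neither a baseline-to-4-week correlation nor a 4-week effect, so r is varied and 0.64 SD is kept. With n = 30 per arm, the noncentrality is [0.64 / √(1 − r²)] × √(30/2), with 60 − 3 = 57 degrees of freedom and critical value 2.002. For r = 0.50 this is (0.64 / 0.866) × 3.873 = 2.862. The last two columns apply the plan's own method: 40 × (1 − r²), rounded up, divided by 0.92, rounded up.

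| Assumed r at week 4 | Noncentrality | Power, 30 per arm | Per group | Total |
|---|---|---|---|---|
| 0.60 | 3.098 | 86% | 29 | 87 |
| 0.50 | 2.862 | 80% | 33 | 99 |
| 0.40 | 2.704 | 76% | 37 | 111 |
| 0.30 | 2.598 | 72% | 41 | 123 |

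If r stayed at 0.50 but the difference at week 4 were 0.5 SD (also an assumption), the noncentrality would be (0.5 / 0.866) × 3.873 = 2.236 and power 59%.

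**4. Cost of an open choice of visit.** Suppose each visit is tested at two-sided 0.05 and success is claimed if either rejects. Type I error is 1 − P(|Z₁| < 1.96 and |Z₂| < 1.96), with Z₁ and Z₂ bivariate normal with correlation ρ. The result is 9.3% at ρ = 0.4, 8.8% at ρ = 0.6 and 7.8% at ρ = 0.8. The values of ρ are assumed. This is for one contrast on one outcome only.

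**The case against.** The strongest reply is that a 4-week comparison is plainly intended: the plan names it as primary twice, so it has not been dropped, only left without a written model. That is fair, and it limits the analyst's freedom. It does not remove the conflict, because the only model on paper uses the other visit and the sample size section repeats that visit independently. This is not a single slip.

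Second, parts of the sample size do apply to week 4. The dropout allowance uses four-week retention, and 0.64 SD is finally adopted as a minimally relevant effect, which need not belong to one visit. Both points stand. The outcome and the justification for r still refer to two weeks, and the needling study behind the 0.64 measured its result one week after treatment.

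Third, the power figures are a sensitivity range and not a demonstrated loss. This is also correct: r could exceed 0.50, and at 0.60 power is 86%. The 8–9% error likewise applies only if either visit may count as success.

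Fourth, placing exercise in weeks three and four is a deliberate design feature, and the visit labels are an editorial matter. Agreed. Neither is a separate defect; they explain why the choice of visit changes the question.

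**Conclusion.** The concern holds and must be fixed. The declared primary time point is 4 weeks, while the only specified efficacy model and the sample size are for 2 weeks. This conclusion rests on the plan's text alone and needs no assumption.

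The numerical consequences are conditional. Type I error of about 8–9% instead of 5% assumes an either-visit claim and a test correlation between 0.8 and 0.4. Week-4 power of 72–80% assumes 30 evaluable per arm, a 0.64 SD difference and r between 0.30 and 0.50. If both 0.64 SD and r = 0.50 hold at week 4, the planned 99 participants are unchanged.

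**What to change.** In Statistical methods, make the 4-week ODI and the 4-week NPRS the dependent variables of the primary ANCOVAs, each with its own baseline value as covariate, for both contrasts (combination against manipulation, combination against needling). Write all of these models out, and list the 2-week models as secondary.

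In Sample size justification, restate the calculation for week 4. Justify the effect size and r over the baseline-to-4-week interval, and show power for r from 0.3 to 0.5. Label every visit in weeks from baseline, matching the schedule in the design overview.

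If the sponsor in fact intended 2 weeks as primary, the design overview and Statistical methods must say so instead. Either way, settle it before anyone sees outcomes by arm.

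The cost is wording: no new visits, data or analyses beyond those already implied. The restated power may be a few points below 80%. The sponsor can accept and report that; holding 80% at r = 0.40 or 0.30 would take 111 or 123 participants by the plan's own method.

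### Each contrast uses one follow-up visit and no missing-data rule is stated; a two-arm repeated-measures model would use the earlier ODI and NPRS scores at little cost

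*Combined protocol and SAP*

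**What the plan says.** Statistical methods promises longitudinal data: "Repeated measurements of the outcomes will be collected at baseline, two weeks post-treatment, and four weeks post-treatment". The opening design description adds a week-1 score, since "All patient-reported outcomes will be assessed 48 hours following the second and fourth treatment sessions", with two sessions a week for two weeks. It also schedules "NPRS and ODI measures taken at the final assessment at the end of the fourth week".

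The analysis does not use this series. For combination versus manipulation, "a linear regression model will be fitted using the 2-week ODI as the outcome variable", with arm as predictor and baseline ODI as covariate. For the other contrast, "In a similar model, (SMT+DN+EXER) will be compared to (DN+EXER"). The same section declares: "The primary time point is at four weeks (late effect) and the secondary time point is at two weeks (early effect"). No week-4 model is written out.

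No section gives an analysis population, a rule for missing outcomes, imputation or a sensitivity analysis. Dropout appears only in Sample size justification, as an enrolment allowance: "Based on prior work of 92% retention to a four-week trial".

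Under Intervention groups, the second half of the trial is unsupervised: "Participants will continue to perform the assigned exercises through the third and fourth weeks at home up until the final assessment".

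**The concern.** An ordinary regression on one visit silently drops everyone who lacks that visit. Clinic treatment ends at week 2 and the next contact for outcomes is week 4. Anyone lost during the home-exercise phase would normally already have week-1 and week-2 scores, and a week-4 ANCOVA would ignore them.

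Three things are at stake. Some precision is thrown away. If dropout is related to early response and differs between arms, the completer contrast is biased. And because no rule is stated, the handling of missing scores could be settled after the data are seen.

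**Working it through.** **Inputs from the documents.** Effect 0.64 SD, two-sided alpha 0.05, power 80%, baseline-to-follow-up correlation 0.50, retention 92%, 33 per group (all Sample size justification, except that alpha is also in Statistical methods).

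**Inputs assumed (not in the documents).** Correlation *r* between follow-up visits of 0.5, 0.7 or 0.9; the timing of dropout; dropout by arm; and what drives it.

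**1. The plan's sample size.** By noncentral t, 40 per group gives power 0.807 without adjustment (the plan writes both 41 and 40). Then 40 × 0.75 = 30, 30 / 0.92 = 32.6, rounded up to 33, and 3 × 33 = 99. The figure reproduces.

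**2. Who would be omitted.**
- Week 4: 99 × 0.08 = 7.9 trial-wide; 66 × 0.08 = 5.3 per two-arm contrast.
- Week 2: 92% is retention over four weeks, so the loss by week 2 lies between 0 and 8 of 99, and only week-1 scores could help.

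**3. Completer power at week 4.** 33 × 0.92 = 30.4 per arm. Residual variance is 1 − 0.50² = 0.75, so SE = √(2 × 0.75 / 30.4) = 0.222 SD. Power is 0.808 (0.803 at exactly 30 per arm; 0.840 with no dropout).

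**4. Precision gain from earlier scores.** Using week 2 only, the ratio of likelihood variance to completer variance is

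[R²/n₂ + (1 − R²)/0.92] ÷ [1/0.92], with R² = ((r − 0.25)/0.75)²,

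where n₂ is the share of randomised participants with a week-2 score.

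| r | R² | all dropouts have week 2 | half do | none do |
|---|---|---|---|---|
| 0.5 | 0.11 | 0.991 | 0.995 | 1.000 |
| 0.7 | 0.36 | 0.971 | 0.985 | 1.000 |
| 0.9 | 0.75 | 0.940 | 0.969 | 1.000 |

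Power in the first column is 0.812, 0.820 and 0.832. A small-sample simulation (33 per arm, 8% missing at week 4) gave ratios 0.992, 0.972 and 0.933. If all dropouts also have week 1, with the same correlation between all follow-up visits, the ratios are 0.987, 0.964 and 0.936 and power is 0.813, 0.823 and 0.834. With no follow-up score at all, nothing is gained.

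**5. Bias, dropout driven by the observed week-2 score.** Simulation with 1,000,000 per arm, true effect 0.64 SD, and odds of dropout multiplied by 2.7 per SD. Entries run over r = 0.5, 0.7, 0.9.
- Single-treatment arm 12%, combination 4%, poor responders leave: completer effect understated by 2.7, 5.0, 7.1%.
- Same rates, good responders leave: overstated by 2.7, 4.9, 7.1%.
- Rates reversed between arms: the signs swap, with similar size.
- Half of the dropouts leave at random before any follow-up score: 1.5 to 4.1% in size.
- Equal 8% dropout: near zero, within simulation error.
- The likelihood model is within simulation error of zero where dropout is driven by the week-2 score, as it must be, because this pattern meets its own assumption.

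The largest of these in ODI points: 0.07 × 0.64 = 0.045 SD, and 0.045 × 12.6 = 0.6 points, against an SE of 0.222 × 12.6 = 2.8 points.

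**6. Bias, dropout driven by the unobserved week-4 score.** With the same 12% versus 4% and the same odds, completer bias is about 8% at every r. The likelihood model leaves about 7% at r = 0.5, 5-6% at 0.7 and 2% at 0.9. It helps, but only in part.

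**The case against.** Enrolment was raised from 30 to 33 per group precisely because of expected dropout, and 30.4 completers meet the required 30. Baseline-adjusted completer ANCOVA is a standard analysis and is unbiased if dropout depends only on arm and baseline. The bias figures need several assumptions at once: at 33 per arm, 12% versus 4% is about four people against one. Even then the bias is under a quarter of one standard error. The written model and the sample size also both refer to week 2, so a week-4 ANCOVA is an inference from the declared primary time point.

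All of that stands, and it fixes the size of the point. It does not remove it. A larger sample protects power, not against dropout that is related to response and differs by arm. And no missing-data rule is given for either visit.

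Three stronger readings are tempting and not supported:
- *The trial loses its planned power.* It does not; completer power is about 81%.
- *The result will be biased in a known direction.* The documents give no dropout by arm, no mechanism and no correlation between follow-up visits, so neither size nor sign can be settled.
- *A repeated-measures model solves the missing-data problem.* It relies on missing at random, and step 6 shows what remains when that fails.

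**Conclusion.** The point holds as a cheap improvement of low severity. The plan specifies single-visit ANCOVAs and is silent on missing scores, while collecting earlier scores that could be used.

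The benefit ranges from nothing (no dropout has a follow-up score) to about 6% less variance and power of about 83%. Completer bias ranges from near zero with equal dropout to about 3-7% of 0.64 SD under the assumed 12% versus 4% split driven by the week-2 score. A likelihood model removes that bias, but only reduces it (from about 8% to about 2-7%) if dropout depends on the unseen week-4 score. These ranges rest on assumed correlations of 0.5 to 0.9 and assumed dropout patterns. The omission counts rest on the plan's 92% retention.

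Which visit is primary is a separate inconsistency, and this point does not decide it.

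**What to change.** For ODI and NPRS, replace the single-visit regression in each two-arm contrast with a baseline-adjusted mixed model for repeated measures on weeks 1, 2 and 4: arm × visit, baseline × visit, unstructured covariance, Kenward-Roger degrees of freedom. Include everyone randomised who has any post-baseline score. Take the contrast at whichever visit is confirmed as primary once the week-2 and week-4 statements are reconciled. Fitting per two-arm contrast avoids borrowing an equal-variance assumption from the third arm.

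State the missing-at-random assumption. Report two sensitivity analyses: the completer ANCOVA, and a simple delta adjustment for departures from missing at random, which the completer analysis cannot test. Tabulate dropout timing and reasons by arm.

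The cost is a few lines of SAP text and standard software, with no new visits or data. The downsides are slightly more modelling work, reliance on missing at random, and no help for people with no follow-up score.
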